Treatment will occur over a 6-week period with daily participation. Treatment-related procedures will last up to one hour per day. In addition to the treatment itself, children's language will be sampled periodically to determine which aspects of speech and language are in error and should be treated, as well as to track progress. Testing of verbal and nonverbal characteristics are obtained during the treatment period for 15 additional minutes approximately twice a week. To facilitate participation of low SES children [whose parents cannot miss work for their child's treatment], all children will be offered supervised day care, provided separately from the treatment, for up to 5 hours per day. Parents are

asked to return with their children between 2 and 4 months post treatment to measure retention of treatment effects.

This study will compare two variants of the same treatment. In one, children will be told the meaning of verbs that they will be prompted to use along with their grammatical target. In the other, children will not receive information on word meanings.

Treatment sessions will be audio and video recorded. This will apply to all children as a condition of participation. The recordings are needed to assess accuracy of treatment delivery and accuracy of the coding of children's responses to the treatment. We will request permission to use video recordings for training future students and clinicians. Consent will be indicated by the parent's initials on a line giving this consent on the PHI consent form. This consent is not required for the child to participate.

Participant qualification testing includes:

A pure-tone audiometric screening.

The nonverbal scales of the Kaufman Assessment Battery for Children. materials appended

The Structured Photographic Language Test (monolingual English speakers) or the BESA (English/Spanish bilinguals). materials appended

Treatment methods:

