Treatment methods occur in an adult-child context in which the two are engaged in child-appropriate activities (e.g., board games, structured play, book reading, craft projects) and conversation. This treatment is known as Conversational Recast which is known to have an overall positive impact on children's language skills, based on published research by our group and others (going back into the early 1980s) Clinicians elicit language from the child by prompting them to use particular words, phrases, or sentences. After a child's response to the clinician's prompt, the clinician provides a correct model of the child's attempted utterance. Children are provided with at least 24 opportunities per session to attempt a treatment target and to receive feedback in the form of a correct repetition of the utterance or praise. No negative feedback is used.

It is not possible in advance to provide the exact words, phrases, or sentences used in treatment for multiple reasons. First, the linguistic units targeted for treatment are tailored to the errors of omission or commission for each individual child enrolled. These are never uniform across all children. Second, research considerations such as balancing particular targets across treatment groups influence the decision on what to treat, and therefore, the words used. Third, the treatment is not scripted and should not be scripted (scripted treatments have yielded poor effects in the previous literature). Fourth, our previous research has found that clinicians must use a large variety of words and contexts to train language for it to generalize to new linguistic and environmental contexts. It is not unusual for clinicians to use 75 different activities and well over 200 different

target words over the course of a treatment period. Finally, since treatment occurs in a conversational context with the child, treatment doses (the words spoken to children thought to effect change) often follow from what the child says, which is not predictable in advance.

Sessions are video and audio recorded so that the accuracy of treatment administration and coding of child utterances can be checked. These are used so that paper records can be checked for accuracy against a recorded record. Entire sessions are never transcribed, although individual words may be when it is important to record the exact sounds used in a child's production (e.g., him vs. he; bringed vs. brought, wabbit vs. rabbit).

Analysis plan

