In this study, the dependent variable is expressed as change from baseline performance in units of standard deviation. This was designed to address the question of whether the treatment produced positive change overall. For this, we consider performance on the generalization probes from the first three pretreatment and final three end-treatment probe sessions. We calculate a single-subject effect size d metric that reflects gains in morpheme use from baseline levels, for each individual child. This is calculated for each of the Target and Control morphemes as follows:

$$\text{Generalization } d = \frac{(\text{end treatment probe mean} - \text{pretreatment probe mean})}{\text{end treatment standard deviation}}$$

We note that when the end treatment standard deviation was zero, we used the minimum possible standard deviation to avoid dividing by zero. We will compare the effect sizes of Target morpheme use to Control morpheme use for each group to determine the effects of treatment in terms of generalization to untreated words.

We used a Bayesian statistical approach to data analysis, using JASP software (JASP Team, 2021). For all tests, we will use the Bayesian equivalent of a Mann-Whitney U test for between group comparisons and a Wilcoxon signed-rank test for within-subject comparisons. Bayesian statistics do not require data to meet the assumptions of other parametric tests (e.g., t-tests), which the types of small samples used in early efficacy studies are unlikely to meet. Another important difference is that Bayesian statistics do not test for statistical significance but express the probability that two distributions are different. This probability is expressed as a Bayes Factor (BF), which can range from 0 to infinity, signaling that probability of a difference is highly unlikely to near certainty. A Bayesian approach can also evaluate the probability that two distributions are equivalent ($1/[BF]$ for group differences), which is not possible for traditional parametric statistics. For tests of within- or between-group differences, this expresses the range of effect sizes from within which the true effect is likely to fall. For correlations (Kendall's tau here), it expresses the range of correlations from which the true correlation is likely to fall.

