As BFs increase above 1.0, support for the experimental hypothesis (e.g., group or condition differences) also increases. Guidance on the strength of support was provided by van Doorn et al., (2021), who suggested that BFs between 1 and 3 can be interpreted as providing

weak or incremental support for a hypothesis, moderate support indicated by BFs between 3 and 10, and strong support for BFs above 10. Although these values were suggested in the context of experimental research. We note, however, that comparison of two treatment methods that are each known to be efficacious, as will be the case here, is unlikely to result in a BF large enough to meet this criterion for “strong support”.

To address the effectiveness of the treatment, we will compare the treatment d for treated and control grammatical forms, collapsed across treatment conditions. To address whether providing semantic support improves learning, we will compare the treatment d for children who did and did not receive semantic support during treatment. To address the degree to which children retained learning after treatment concluded, we correlated (Bayesian Kendall’s Tau) the mean performance on the average of the final 3 generalization probes with performance at follow-up.

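### Should the semantic-support comparison be corrected for each child's Control d, given that no assignment rule is stated?

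*Combined protocol and SAP*

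**What the plan says.** Section 3 of the combined document gives the purpose: "This study will compare two variants of the same treatment". One variant explains the meanings of the verbs used; the other does not.

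The Analysis plan defines d as the mean of the last three end-treatment probes minus the mean of the first three pretreatment probes, divided by the end-treatment SD. "This is calculated for each of the Target and Control morphemes as follows", so every child has both a Target d and a Control d.

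Control d is then used in two places:
- by variant: "We will compare the effect sizes of Target morpheme use to Control morpheme use for each group";
- pooled, for overall effectiveness: "we will compare the treatment d for treated and control grammatical forms, collapsed across treatment conditions".

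The semantic-support question is handled separately: "we will compare the treatment d for children who did and did not receive semantic support during treatment". The test is "the Bayesian equivalent of a Mann-Whitney U test for between group comparisons", which takes one score per child and no covariate. I read treatment d here as d on the Target form.

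No section describes how children are allocated to a variant. The one balancing statement, under Treatment methods, concerns forms and not children: "research considerations such as balancing particular targets across treatment groups influence the decision on what to treat".

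**The concern.** Children may be anywhere from 4;0 to 6;11, and language development at those ages need not run at one pace. Subtracting a child's baseline removes starting level, at least in part. It does not remove growth during the treatment period. Control d is the plan's own measure of growth without treatment, yet the contrast that answers the new question leaves it out.

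The plan also expects a small difference between variants: it says that such a comparison "is unlikely to result in a BF large enough to meet this criterion" for strong support. Conclusions will then probably rest on weak or moderate Bayes factors, where a modest difference in growth could pass for a benefit of semantic support. If children were not randomised, nothing in the stated design or test would separate the two.

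**Working it through.** **1. The stated sample size.** Section 1 gives 16 to 24 children per study, with no alpha, power, effect size or SD, so the figure cannot be reproduced. I assume it is a total split equally: n = 8 or 12 per variant. At an assumed two-sided 0.05 and 80% power, the detectable difference is (1.96 + 0.84) × √(2/n) = 1.40 SD (n = 8) or 1.14 SD (n = 12). If 16 or 24 is per variant, it is 0.99 or 0.81 SD.

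**2. If assignment is random.** The chance difference in mean growth has SE √(2/n) = 0.50 SD (n = 8) or 0.41 SD (n = 12). It exceeds 0.5 SD with probability 2[1 − Φ(0.5/SE)] = 32% or 22%. For age spread evenly over 36 months, the SD is 36/√12 = 10.4 months and the SE of the difference is 5.2 or 4.2 months; a gap above 6 months occurs in 25% or 16% of studies. These are large, but they are sampling noise that the test already allows for. The contrast is valid without Control d.

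**3. If assignment is not random.** As a rough guide, take a two-sided 0.05 test and a growth difference of g SDs of Target d. The false-finding rate is 1 − Φ(1.96 − g/SE) + Φ(−1.96 − g/SE). At g = 0.5 this is 17% (n = 8) or 23% (n = 12), instead of 5%.

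A simulation on the plan's own d is closer to what will be done. None of its inputs is in the documents:
- 10 or 20 items per probe;
- baseline logit mean −1.5, SD 0.7;
- child growth shared by both forms, mean 0.7 and SD 0.7 logit;
- form-specific growth SD 0.3 or 0.7;
- treatment adds 1 logit to the Target form in both variants;
- the test is approximated by a t statistic on ranks, with the cut for a Bayes factor of 3 at t = 2.484 (12 per variant, default prior scale 0.707, since no prior is stated).

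Imbalance is in SDs of child growth. Only results favouring the faster group are counted. Ranges span the four settings; separate runs differ by a point or so.

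| Rule for claiming support (12 per variant) | False support, 0.5 SD imbalance | False support, 1 SD imbalance |
|---|---|---|
| Target d, BF > 3 (as planned) | 4.5-5.7% | 12.8-16.8% |
| Same, and Target minus Control d has the same sign | 4.3-5.3% | 11.6-15.1% |
| Target minus Control d replaces Target d, BF > 3 | 1.4-1.7% | about 2% |

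With no imbalance, the planned test gives about 1.2%. Agreement in sign barely helps, because a false result on Target d pulls the difference score the same way.

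**4. The price of the rules that do protect.** Take an assumed true semantic effect of 1 logit and no imbalance.
- BF > 3 on both scores: false support at 0.5 SD falls to 0.7-0.8%, but detection falls from 26-33% to 12-21%.
- Replacing Target d by the difference: detection goes from 27-34% to 22-34%.

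**5. Dependence on the growth assumption.** Treatment lasts six weeks. With growth mean and SD of 0.2 logit instead of 0.7, a 0.5 SD imbalance gives false support in only about 2-2.5% of studies, against 1.2% with none. Replacement then cuts detection from 36-55% to 20-38%.

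**6. Precision.** If both forms have the same SD and within-child correlation ρ, the variance relative to Target d alone is 2(1 − ρ) for the difference and 1 − ρ² for covariate adjustment. Subtraction gains only if ρ > 0.5. In the 0.7-logit settings the rank correlation is about 0.23 to 0.43, which gives:
- difference: 2 × 0.77 = 1.54 to 2 × 0.57 = 1.14, so variance rises by 14-54%;
- adjustment: 1 − 0.053 = 0.95 to 1 − 0.185 = 0.82, a gain of 5-18%.

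Adjustment would need a different test. It also conditions on an outcome measured after treatment starts, which could absorb part of the effect if semantic support spills over to the Control form.

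**The case for a change.** The strongest case for a change is this. A study whose main new question is between children should say how they are assigned, and this one does not; the procedures and analysis text are present and silent. Baseline subtraction does not deal with growth rate. Comparing Target with Control in each group gives two separate results, which do not test the difference between variants. A companion analysis would use values already computed and need no new data.

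The factual parts stand. The inference to a change does not. Silence on assignment does not show that assignment was non-random, and if it was random, leaving out Control d is a choice about precision. A companion that only has to agree in sign protects almost nothing. One with a real threshold costs much of the power of a small study.

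A related point is that the documents do not say how a form becomes Target or Control, so the effectiveness contrast could in principle compare two different forms. That is a separate contrast and no size can be put on it. Treatment methods says that targets are fitted to each child's errors and differ between children, so the extreme case of one Target form for everyone is not this design.

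**Conclusion.** No change to the plan follows. Two things are true: the semantic-support contrast omits Control d, and the assignment rule is not stated. The second is a gap in description that the study's analysts can fill from what was actually done, and that would limit causal wording if assignment proved not to be random. The first is a fair trade-off. Working on change from the child's own baseline leaves growth rate, the end-treatment SD and scope for gain as routes for a group difference, and these bias the result only under non-random assignment. Because Target and Control are already compared within each variant, a group whose untreated forms also grew faster should be visible in the planned results.

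The possible inflation is about 5-6% against 1.2% for a Bayes factor above 3 at a 0.5 SD imbalance, or 2-2.5% if growth over six weeks is smaller. These rates assume 12 per variant, probe lengths, growth values and a prior that the documents do not give. The size and direction of any real imbalance are unknown. Against that uncertain gain, the versions of the correction that work lose sensitivity in most settings examined.

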Brief Title: Training Grammar With Meaning

Unique Protocol ID: DLD-Tx2

ClinicalTrials.gov Identifier: NCT06250101

September 8, 2025

1) Study Population

Participants will be between the ages of 4 and 6 years old and have a language impairment. Children will include both boys and girls. Given that boys are more often affected by this condition, we expect a slight excess of boys in the sample (e.g. 2:1 m:f). Subjects will be recruited from Tucson area preschools, kindergartens, daycare centers, and treatment programs. We intend to sample from geographic regions that are likely to produce a diversity of racial and ethnic backgrounds.

We anticipate that up to 300 children will participate over 6 years. Children will reflect all socio-economic levels (as indexed by mother's/guardian's educational level) with racial and ethnic distribution roughly equivalent to that of the Tucson population of children.

Power analyses indicate that between 16 and 24 children are required per study to find significant effects. Sample sizes may be adjusted to reflect actual effects as studies proceed. To get these numbers, we typically need to test 50 participants a year, with children not meeting the criteria for language impairment, children having insufficient numbers of potential treatment targets (speech/language errors) withdrawn after testing.

Inclusion criteria include:

Between ages 4 years 0 months and 6 years 11 months at the time of treatment onset.

Native English language development, with exposure to other languages acceptable.
Normal hearing as indicated by a pure-tone audiometric screening.

Normal nonverbal skills as indicated by the nonverbal scales of the Kaufman Assessment Battery for Children.

Impaired language as indicated by the Structured Photographic Language Test (monolingual English speakers) or the BESA (English/Spanish bilinguals).

Exclusion criteria include

Other handicapping conditions that could cause poor language skills (e.g., autism, intellectual disability, blindness, genetic disorders, neurologic disease or injury), by parent report.

Native language skills other than English.

Lack of functional English proficiency by *both* parents or *any* guardian.

2) Recruitment Methods and Consenting Process

a. Recruitment Process:

- 1) Recruitment flyers will be provided through preschools and daycares that include children with language impairments. The flyer is attached.

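### Retention is assessed only by a rank correlation between end-of-treatment and follow-up scores, which cannot show how much learning was lost: tau can be 1 when most of the gain has gone.

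*Combined protocol and SAP*

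**What the plan says.** Section 3 (Research procedures) gives the reason for the follow-up visit: parents are "asked to return with their children between 2 and 4 months post treatment to measure retention of treatment effects".

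The last paragraph of the Analysis plan turns this into one of three analysis questions. It opens with "To address the degree to which children retained learning after treatment concluded" and answers with a single statistic, a Bayesian Kendall's tau between "the mean performance on the average of the final 3 generalization probes with performance at follow-up".

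Three other statements in the Analysis plan bear on the point:

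- The effect size d is built from "performance on the generalization probes from the first three pretreatment and final three end-treatment probe sessions". Follow-up scores do not enter it, and the other two analysis questions are both answered with d.
- The plan names "a Wilcoxon signed-rank test for within-subject comparisons", in its Bayesian form, but does not assign it to end of treatment versus follow-up.
- For correlations, the plan describes the output in these words: "it expresses the range of correlations from which the true correlation is likely to fall". That is a range for a correlation, not for an amount kept or lost.

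No paired change, retained proportion, or comparison of follow-up with pretreatment is planned.

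**The concern.** The degree of retention is a question about level: is performance at 2 to 4 months as high as at the end of treatment, and how far above baseline is it still? Kendall's tau answers a different question, namely whether the children who scored higher at the end of treatment also score higher at follow-up. The two can disagree in both directions. Children can all decline in step and keep their order, which gives a high tau with large loss. Or they can all stay at a similar high level and swap places through noise, which gives a low tau with no loss.

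Pretreatment scores do not enter the correlation either. A positive tau may therefore reflect stable differences between children that were there before treatment, rather than anything learned.

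What is at stake is the conclusion drawn from the follow-up visit. A large Bayes factor for tau could be read as evidence of retention when most of the gain has gone, and a small one as poor retention when nothing was lost.

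**Working it through.** The plan states no figure for the retention analysis, so there is none to reproduce. The check concerns a property of the statistic. All score values below are assumptions, because the documents give no score distribution, probe length or measurement error. The number of children is taken from or set within the 16 to 24 per study stated in section 1 (Study Population).

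**1. The algebra.** Tau = (concordant pairs − discordant pairs) / all pairs, when there are no ties. A pair of children is concordant if the one with the higher end score also has the higher follow-up score. If follow-up is any strictly increasing function of the end score, every pair is concordant and tau = 1, however low the follow-up scores are.

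**2. Loss as a share of the end level, no noise.** n = 20, end scores evenly spaced from 20% to 95%, mean 57.5%.

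| Follow-up score | Mean at follow-up | Tau |
|---|---|---|
| unchanged | 57.5% | 1.00 |
| × 0.5 | 28.75% | 1.00 |
| × 0.2 | 11.5% | 1.00 |
| − 15 points | 42.5% | 1.00 |

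**3. Loss as a share of the gain, no noise.** Follow-up = pre + r × (end − pre), where r is the share of the gain kept. Take a common baseline of 0.05 and end scores from 0.20 to 0.95 (mean 0.575). At r = 0.2 the mean at follow-up is 0.05 + 0.2 × (0.575 − 0.05) = 0.155. Tau is 1.00 at r = 1, 0.5, 0.2, 0.1 and 0.01, for n = 16 and n = 24. At r = 0.01 the mean is 0.055, almost back to baseline.

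A paired signed-rank test (frequentist stand-in for the Bayesian version) on the r = 0.2 data gives p = 2/2^16 = 3.1e-05 at n = 16 and 2/2^24 = 1.2e-07 at n = 24. These are the smallest values possible, because every child declines.

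**4. With measurement noise.** n = 20, independent noise of SD 5 points at both visits, 2,000 simulated studies, follow-up true score a fixed share of the end true score.

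| Share of end level kept | Mean tau, true end scores drawn uniformly from 20–95% | Mean tau, true end scores evenly spaced |
|---|---|---|
| 100% | 0.80 | 0.85 |
| 40% | 0.65 | about 0.70 |

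On the evenly spaced data, the paired signed-rank test at the 5% level flagged the 60% loss in 100% of runs and flagged full retention in about 5%.

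**5. Baselines that vary independently of gain.** With baseline SD from 0.02 to 0.10 and 20% of the gain kept, mean tau runs from about 0.74 down to 0.54. It is lower than 1 but clearly positive, although four fifths of the gain is gone.

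**6. Complete loss.** Suppose every child returns exactly to baseline. Tau is then the correlation between baseline and end score. For bivariate normal scores, tau = (2/π) × arcsin(ρ): 0.19, 0.33 and 0.49 for assumed ρ of 0.3, 0.5 and 0.7.

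**7. The converse.** If all 20 children have a true level of 90% at both visits, with independent noise of SD 3 points, mean tau is about 0.00 although nothing was lost. If all children score at ceiling, every pair is tied and tau is undefined.

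**The case against.** The best counter-argument is that tau is not unrelated to loss. An exact value of 1 needs noiseless, order-preserving decline. With measurement error, tau falls as loss grows: in the evenly spaced setting of step 4 it is about 0.85, 0.70, 0.50 and 0.29 when 100%, 40%, 20% and 10% of the end level is kept. Children who lose different amounts also change order, which lowers tau further. This is true, but it does not rescue the analysis. The fall reflects reordering and a shrinking ratio of signal to noise, so the same tau can arise from very different amounts of loss, or from none when the children score alike. No value of tau can be converted into an amount retained.

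A second argument is that the Analysis plan already names a signed-rank test for within-subject comparisons, so a paired test might be thought to be covered. The paragraph on retention, however, names correlation for this question and specifies no end-to-follow-up contrast.

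Third, retention is the last of three questions, and the other two rest on d and are untouched. That limits the reach of the problem but does not make the retention answer valid.

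Two further points stand. The simulated values depend on assumed scores, and the scenario with all children near 90% is chosen to show the converse, not because the documents predict it. The plan also sets no rule that equates a large Bayes factor for tau with retention, so misreading is a risk rather than a certainty.

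**Conclusion.** The concern holds. The only analysis that uses follow-up data is a rank correlation, and the stated question is how much learning was kept. Under order-preserving loss tau is exactly 1.00 with 50%, 80% or even 99% lost. Under the assumed noise, a 60% loss moves mean tau only from 0.80 to 0.65 (0.85 to about 0.70 with evenly spaced scores). Full retention among children who score alike gives a mean tau of about 0.

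The invariance to order-preserving change is mathematical and needs no assumption about the data. The intermediate values rest on the assumed score range, noise and baselines. The correlation does legitimately show whether children keep their relative standing, but that is not the question the plan poses. It should be corrected before the follow-up data are analysed.

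**What to change.** Replace the retention analysis with paired comparisons:

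- **Main analysis:** the Bayesian Wilcoxon signed-rank test on follow-up minus the mean of the final three generalization probes, reported with the median change and its 95% credible interval. State that follow-up performance is scored on the same probe measure and scale, so that the difference is meaningful.
- **Supporting analysis:** the same test on follow-up minus the pretreatment probe mean, for target and control morphemes separately, to show how much of the gain remains and whether it is specific to treated forms. The first comparison alone would show loss. This one shows what is left.
- **Secondary description:** keep Kendall's tau, labelled as a measure of whether children keep their rank order, and state that it is not evidence of retention or loss.

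The cost is a change of SAP wording and one or two extra tests with a method already named in the plan, on data already being collected. No new visits or children are needed.
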